6.4.1 Primary safety variables	19
6.4.2 Supplementary Safety Analysis.....	22
6.4.3 Other safety analyses	22
6.4.4 Subgroup analysis.....	24
6.4.5 Adverse events.....	25
6.4.6 Vital signs.....	26
6.4.7 Laboratory parameter	26
6.4.8 Hemodialysis data	26
6.4.9 Pregnancies.....	27
6.5 Data affected by the regional crisis.....	27
7. Document history and changes in the planned statistical analysis	27
7.1 Version 1.0.....	27

7.2 Version 2.0 27

7.3 Version 3.0 28

7.4 Version 4.0 28

8. References 29

9. Appendix 29

9.1 Determination of sample size 29

9.2 Randomization Methodology 30

9.3 Treatment Assignment Probabilities 31

Table of Figures

Figure 3–1: Study design review 8

Abbreviations

ADA	Anti-drug antibody
AE	Adverse event
AESI	Adverse events of special interest
ALT	Alanine aminotransferase
ANOVA	Analysis of variance
AP	Asia Pacific
aPTT	activated Partial Thromboplastin Time
ASA	Acetylsalicylic acid
AST	Aspartate aminotransferase
ATC	Anatomical Therapeutic Chemical
AV	Arteriovenous
BMI	Body mass index
CARURS	Covariate Adaptive Randomization User Requirements Specification
CI	Confidence interval
CIAC	Central Independent Adjudication Committee
CIF	Cumulative incidence function
CRF	Case report form
CRNMB	Clinically relevant non-major bleeding
cs	cause specific
CSR	Clinical Study Report
CV	Cardiovascular
DMC	Data monitoring committee
eCRF	Electronic case report form
EOMT	End of main treatment phase
EOET	End of extension treatment phase
ESRD	End Stage Renal Disease
FAS	Full Analysis Set
F1.2	Prothrombin fragment 1.2
GCP	Good Clinical Practice
HEOR	Health Economics and Outcome Research
HR	Hazard ratio
ICF	Informed consent form
ICH	International Council for Harmonization
ISTH	International Society on Thrombosis and Haemostasis
IwRS	Interactive web response system
LD	Loading dose
LMWH	Low molecular weight heparin
LOS	Listing only set

LTFU	Lost to follow-up
MACE	Major adverse cardiovascular event
MD	Maintenance/ monthly dose
MedDRA	Medical Dictionary for Regulatory Activities
MI	Myocardial Infarction
NAB	Neutralizing Antibody
N/A	Not applicable
PD	Pharmacodynamic(s)
PE	Pulmonary embolism
PK	Pharmacokinetic(s)
PPS	Per-protocol set
PT	Preferred term
RBC	Red blood cell
RHR	Relative hazard reduction
RRR	Relative risk reduction
SAC	Statistical Analysis Center
SAE	Serious adverse event
SAP	Statistical Analysis Plan
SAS	Statistical Analysis Software
SE	Systemic embolism
SOC	System organ class
SQCS	Semi-quantitative clotting score
TAT	Thrombin-antithrombin complex
TE	Thromboembolic
UFH	Unfractionated heparin
VTE	Venous thromboembolism
WBC	White blood cell

1. Introduction

Osocimab is a novel long-acting anticoagulant targeting the activated form of FXI with the potential to exhibit lower risk of bleeding events than currently available anticoagulants.

It is well known that ESRD patients on dialysis are at high risk for cardiovascular diseases. By targeting FXI, osocimab has the potential to provide an efficacious treatment for the prevention of thromboembolic events like MI, stroke, and cardiovascular death with a favorable risk profile for unwanted bleeding. This Phase 2b trial will assess the safety and characterize the PK/PD profile of two different dose cohorts of osocimab given subcutaneously once a month to subjects with ESRD.

Further information can be found in the clinical study protocol.

2. Study Objectives

Objectives and endpoints are listed in the table below:

Objectives	Endpoints
Primary	

 To clinically assess the safety and tolerability of different doses of osocimab administered subcutaneously once a month during main treatment period as compared to placebo 	
 Composite of major and clinically relevant non-major bleeding events (in alignment with the ISTH guidelines) as assessed by blinded central independent adjudication committee (CIAC) Composite of moderate and severe AEs and SAEs
Secondary	

 To assess the change of key PD parameter from baseline 	
 aPTT, FXIa activity at trough levels after 6 months
Tertiary/Exploratory	

 To clinically assess the efficacy of osocimab during main treatment period To evaluate the anticoagulant effect of osocimab on the extracorporeal blood circuit by the assessment of a semi-quantitative clotting score (SQCS) To evaluate the impact of osocimab on the AV access for subjects with fistulas or grafts To assess key PK parameter To explore additional PK/PD parameters, biomarkers, and biomarker genetics To further investigate the study intervention (i.e. mode-of-action-related effects and / or safety) and to further investigate pathomechanisms deemed relevant to cardiovascular diseases and associated health problems 	
 Composite endpoint consisting of: vascular death [due to MI, stroke, PE, and SE], non-fatal stroke, non-fatal MI, major amputation of vascular etiology, acute limb ischemia, symptomatic VTE and systemic embolism as assessed by blinded central independent adjudication committee (CIAC) Incidence of thrombosis of the arterio-venous grafts or fistulas Semi-quantitative clotting score AV access bleeding score Osocimab trough levels Various biomarkers and biomarker genetics may be explored (e.g. diagnostic, safety, population PK, PD, monitoring, or potentially predictive biomarkers)

Abbreviations: AE = adverse event, aPTT = activated partial thromboplastin time, AV = arteriovenous, CIAC = Central Independent Adjudication Committee, ISTH = International Society on Thrombosis and Hemostasis, MI = myocardial infarction, PD = pharmacodynamic(s), PE = pulmonary embolism, PK = pharmacokinetic(s), SAEs = serious adverse events, SE = systemic embolism, SQCS = semi-quantitative clotting score, VTE = venous thromboembolism

The primary objective is to assess the safety under an osocimab concentration which is expected to be maintained during a chronic treatment. Thus, the attributes constituting the primary estimand are the following:

Population: The population consists of ESRD patients, further defined by the in- and exclusion criteria, who received assigned treatment at least once.

Variable:

- Time from first dose of assigned treatment to treatment emergent major and clinically relevant non-major bleeding events (in alignment with ISTH guidelines) up until 30 days after the last administration of assigned treatment
- Time from first dose of assigned treatment to moderate or severe AEs and SAEs up until 30 days after the last administration of assigned treatment

Treatment: Low/high-dose osocimab or matching placebo on top of standard of care

Intercurrent events: Of interest is the response to treatment while the subject is

- alive (intercurrent event “death”) and
- exposed to assigned treatment (intercurrent event “premature discontinuation of treatment”. Rationale: The primary objective is to assess the safety under an osocimab concentration which is expected to be maintained during a chronic treatment.),

i.e. both intercurrent events are handled using the same strategy “while alive” or “while on treatment”.

Changes in the background therapy etc. will be handled following the treatment policy strategy. Other potential intercurrent events are not anticipated.

Population-level summary: (Cause-specific) hazard ratios comparing each of the osocimab dose groups with the placebo group as estimated from cause-specific Cox proportional hazards models.

Of note, based on the current expert assessment of the COVID-19 Public Health Emergency, it was to be expected that a low number of patients will suffer from (symptomatic) COVID-19. In addition, as ESRD patients visit dialysis centers on a regular basis anyway, no increase in missing data is to be expected. This is why no intercurrent event linked to the COVID-19 Public Health Emergency was accounted for. However, any premature discontinuation will be summarized, and selected analyses will be repeated by (symptomatic) COVID-19 (Yes/No). Also, if occurred, number of missed visits related to the COVID-19 pandemic will be summarized.

3. Study Design

Study 20115 is a covariate-adaptive randomization, double-blind, parallel group, placebo controlled, multi-center study to assess the safety and tolerability of monthly administrations of a low and high dose cohort of osocimab given subcutaneously in ESRD patients on hemodialysis. Here the term hemodialysis includes hemodiafiltration. The overall study design is depicted in the figure below.

Approximately 600 subjects (up to 750) from approximately 150 sites are planned to be randomized and will receive either osocimab (200 subjects on each dose arm), or placebo (200 subjects, i.e. 100 subjects receiving low dose volume placebo and 100 subjects receiving high dose volume placebo).

The following regions are planned to be included: North America, Europe, Asia Pacific.

The planned study will consist of:

- Screening period (visit 1): up to 14 days

- Randomization (visit 2): 1 day
- Pre-treatment period (from visit 2 until visit 4): 7 days
- Main treatment period (from visit 5 until EOMT visit): 6 months
- Extension treatment period (from visit 19 until EOET visit): up to 12 months
- Follow-up period (from visit 32 until visit 35): 4 months after end of treatment (EOMT or EOET)

Informed consent form will be obtained at the beginning of the screening period. During the screening period, subject's eligibility evaluations will be performed. Subjects will be randomized either to osocimab or to placebo using a covariate-adaptive randomization technique (minimization methods) (for details see Section 6.3).

During the pre-treatment period, which will serve as a baseline period, a series of 3 hemodialysis sessions will be performed. Unfractionated or low molecular weight heparin (UFH/LMWH) is allowed as anticoagulation for maintenance of hemodialysis treatment during the whole study duration.

The study intervention will be administered subcutaneously abdominal with one single loading dose at visit 5 and monthly maintenance doses from visit 8 onwards until the end of the extension treatment period with an overall maximum of 18 months of treatment. The main treatment period consists of 6 months of treatment as this time frame is deemed to be the minimum clinically relevant treatment time to assess osocimab as chronic life-time treatment in an appropriate manner and in preparation for Phase 3.

Study intervention will be administered during the extension treatment period for up to a maximum of 12 months or until the last subject randomized to the study has performed the EOMT visit (whichever comes first).

The treatment period (main or extension) will end with the study assessments performed 30 days after the last study intervention administration.

The follow-up period is an observational period of 4 months, i.e. ends approximately 5 months after the administration of the last dose of osocimab.

[figure not shown]
All suspected bleeding and cardiovascular (CV) or thromboembolic (TE) events occurring after signing informed consent (randomized subjects only) will be adjudicated by the CIAC in a blinded fashion; blinded to treatment allocation and dose cohort (details are described in the CIAC charter).

The procedures followed by the CIAC are detailed in the CIAC charter. Detailed instructions regarding documentation, reporting and transfer of adjudication dossiers will be provided in a study specific guidance document.

A DMC will frequently review safety data to ensure the safety of the subjects in the ongoing study. Further details can be found in the DMC charter.

Details of study procedures and their timing are summarized in the clinical study protocol.

Figure 3–1: Study design review

Abbreviations: EOET = end of extension treatment phase, EOMT = end of main treatment phase, LD = loading dose, MD = maintenance/ monthly dose, pts = participants, R = randomization, V = visit

The Follow-up ends 5 months after last study intervention and 4 months after EOMT or EOET.

3.1 Randomization and Blinding

Subjects will be randomized between osocimab low dose and placebo low dose and osocimab high dose and placebo high dose in a ratio of 2:1:2:1. Covariate-adaptive randomization techniques, or better the Pocock and Simon Minimization with Biased-coin Assignment methodology (Pocock, SJ, R Simon. ‘Sequential treatment assignment with balancing for prognostic factors in the controlled clinical trial’, Biometrics, 31, pp 103–115, 1975) will be utilized to perform subject randomization for this study.

In brief, each subject’s randomization is performed by calculating the imbalance that will exist by assigning each treatment group in turn – by considering the previous treatment assignments to pre-specified balancing factor levels corresponding to the subject being randomized, and summing the individual factor level imbalances to determine which treatment(s) have minimal imbalance. The treatment assignment for this subject is then performed in a non-deterministic manner, by assigning probabilities of treatment assignment to each of the treatment arms based on the calculated treatment imbalances.

More detailed information can be found in sections 9.2, 9.3 and in the Covariate Adaptive Randomization User Requirements Specification (CARURS) as provided by the IwRS provider ALMAC Clinical Technologies.

The following baseline covariates will be taken into account:

- Region (categorical)
- Age (<50yrs/>=50-<60yrs/>=60-<65yrs/>=65-<70yrs/>=70-<80yrs/>=80yrs)
- Prior major adverse cardiovascular event (MACE) (Yes/No)
- Dialysis access via catheter (Yes/No)
- Low-dose ASA use (Yes/No)

- Diabetes (Yes/No)
- Atrial fibrillation (Yes/No)

The first five covariates will have twice the factor weight than the latter two.

Sponsor, subjects, and investigators are being blinded with respect to active treatment versus placebo, but not blinded to dose cohort (low or high dose). In order to reduce any risk which could be associated with the open-label nature of the dose cohort, the final SAP will be available before first patient first visit. No ad hoc interim analyses comparing the treatment effect of the two dose cohorts will be performed. Aggregation of treatment-specific interim results will only be performed for safety measures in the context of DMC meetings.

The CIAC will remain blinded to the subject's treatment allocation and dose cohort throughout the course of the study. The DMC is unblinded.

4. General Statistical Considerations

4.1 General Principles

The statistical evaluation will be performed by using the software package SAS release 9.2 or higher (SAS Institute Inc., Cary, NC, USA) or other software if applicable. All variables will be analyzed by descriptive statistical methods. The number of data available and missing data, mean, standard deviation, minimum, quartiles, median, and maximum will be calculated for metric data. Frequency tables will be generated for categorical data.

In general, subjects receiving placebo in either the low dose or the high dose cohort will be analyzed in a pooled manner. This group will be referred to as placebo group. The group of subjects receiving osocimab in the high dose cohort (or low dose cohort) will be referred to as high dose (or low dose) osocimab group.

4.2 Handling of Dropouts

A subject may withdraw from the study at any time at his/her own request or may be withdrawn at any time at the discretion of the investigator for safety, behavioral, compliance, or administrative reasons. This is expected to be uncommon.

At the time of discontinuing from the study, if possible, an early discontinuation visit should be conducted. The subject will be permanently discontinued both from the study intervention and from the study at that time. If a subject permanently discontinues/withdraws from the study and is unwilling or unable to attend regular study visits at the study site, all possible efforts should be made to obtain information on the health status of the subject.

A subject will be considered lost to follow-up if he/she repeatedly fails to return for scheduled visits and is unable to be contacted by the study site. The following actions must be taken if a subject fails to return to the clinic for a required study visit:

- The site must attempt to contact the subject and reschedule the missed visit as soon as possible and counsel the subject on the importance of maintaining the assigned visit schedule and ascertain whether or not the subject wishes to and/or should continue in the study.

- Before a subject is deemed lost to follow up, the investigator or designee must make every effort to regain contact with the subject (where possible, 3 telephone calls and, if necessary, a certified letter to the subject's last known mailing address or local equivalent methods). These contact attempts should be documented in the subject's medical record.
- Should the subject continue to be unreachable, he/she will be considered to have withdrawn from the study.

In both cases, when the subject permanently discontinues/withdraws from the study or the subject is lost to follow-up, he/she is considered a dropout. The number of dropouts for any reason, as well as the reasons for dropout, will be displayed by treatment arm. Baseline characteristics will be displayed by dropout (yes/no). All data collected until the dropout will be analysed. Of note, subjects who drop out because they suffer from COVID-19 will be displayed here with the corresponding reason.

In rare instances, it may be necessary for a subject to permanently discontinue (definitive discontinuation) study intervention. If study intervention is definitively discontinued, the subject will remain in the study to be evaluated until the end of the follow-up period. If a subject permanently discontinues study intervention and is unwilling or unable to attend regular study visits at the study site, all possible efforts should be made to obtain information on the health status of the subject. The reason for discontinuation of study intervention must be recorded in the eCRF and source documentation.

The number of subjects who permanently discontinue (definitive discontinuation) study intervention and the reason for discontinuation will be displayed by treatment arm. Baseline characteristics will be displayed by permanently discontinue study intervention (yes/no). All data collected until the discontinuation will be analysed according to the treatment emergent definition.

4.3 Handling of Missing Data

All missing or partial data will be presented in the subject data listing as they are recorded on the Case Report Form (CRF).

General rules

When appropriate, the following rules will be implemented so as not to exclude subjects from statistical analyses due to missing or incomplete data:

- **Efficacy and Safety clinical variables, adverse events**
For cases where start month and year are reported but day is missing, impute the maximum of (date of randomization + 1 week, first date of study intervention, 01.month.year). For cases where only start year is reported, impute the maximum of (date of randomization + 1 week, first date of study intervention, 01.01.year), but not later than death date if the patient died.
- **PD variables**
No imputation will be done for pharmacodynamic parameters.
- **Study intervention start date**
If the start date and time is missing it will be imputed with the randomization date + 1

week and time. If start date and time is recorded as earlier than randomization and cannot be clarified, date and time of randomization will be used for the statistical analysis.

- **Study intervention stop date**

If the stop day is missing, but the stop month and stop year are available then the stop date will be imputed as minimum of (15.month.year and last study visit date in main treatment or extension treatment period and death date).

If the stop day and month are missing then the stop date will be imputed as minimum of (the last study visit date before the post treatment follow-up period and death date).

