For the analysis of the primary endpoint in this study, the hazard function  $h(t)$  is the chance that an individual experiences an event of the primary safety outcome in the next instant in time, given that the individual has not had such an event up to time  $t$ . For example, for the comparison of the osocimab high dose group with the placebo group, the corresponding Cox proportional hazards model can be described by the following equation:

$$h(t, x_i) = h_0(t) \exp(\beta x_i),$$

where

- $h(\cdot)$  hazard function for primary safety outcome, as a function of time and participant's covariates
- $h_0(\cdot)$  unspecified underlying baseline hazard function for primary safety outcome; hazard of an individual with  $x_i = 0$
- $t$  time (in days) relative to the date of first study intervention
- $x_i$  treatment group of participant  $i$   
(0 corresponds to "placebo group" and  
1 corresponds to "osocimab high dose group")
- $\beta$  unknown parameter (to be estimated); hazard ratio =  $\exp(\beta)$

Only events that started after the first dose of study treatment and during the main treatment period are considered for the primary analysis. Events that occurred during the pre-treatment period will be displayed in an exploratory manner.

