4.5 Data Rules

The pre-treatment period serves as baseline period and takes place before first study intervention was given. If there is more than one measurement, the mean of the respective measures will serve as baseline.

Baseline for PD will be visit 5 data prior to dosing.

The primary analysis will be based on all respective events that occurred during the scheduled main treatment period.

Additional analyses may be based on all respective events that occurred during the overall study period, consisting of both the main treatment and extension treatment period.

In addition, further analyses may be based on all events occurring during the full study period consisting of the main treatment, extension treatment and post-treatment follow-up period.

These time scopes are summarized in the table below.

An event is considered treatment emergent if it occurred between start of treatment and not later than 30 days after last administration of study intervention.

An event is considered as full study treatment emergent if it occurred between first study intervention and not later than 5 months after last administration of study intervention.

Additional analysis may be performed post-hoc.

Time scope definition:

Overall study period	Main treatment phase + extension treatment phase
Full study period	Main treatment phase, extension treatment phase + follow up

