6.4 Safety

6.4.1 Primary safety variables

The composite of major bleeding (MB) and clinically relevant non-major bleeding (CRNMB) events, as assessed by CIAC, and the composite of moderate and severe AEs and SAEs will

be the primary safety endpoints in this study. Only events that started after the first dose of study treatment and during the main treatment period are considered for the primary analysis.

For the primary safety analysis descriptive time to first primary safety event (both treatment emergent AEs and composite of treatment emergent major and CRNMB events [in alignment with ISTH guidelines]) analyses will be performed.

According to the description of the primary estimand, the following events will be considered as competing events for the respective safety endpoint:

- death
- premature end of exposure to assigned treatment (last administration of assigned treatment plus 30 days).

For the primary analysis, the time to event for a subject will be censored at the date of the EOMT visit or after no further data collection happened for a subject (e.g. lost to follow-up).

According to the study protocol (section 7.1.1) one maintenance dose can be missed. If a subject misses a maintenance dose, has a so called administration gap, that lasts longer than 30 days, the subject is not considered at risk for treatment-emergent events during this time until the next dose. When the subject then takes a maintenance dose again, he/she is at risk again. Accordingly there will be additional analyses, where the time not under exposure between two doses will be ignored and events during that time will not be counted. The time under risk will be calculated by removing time between the interrupted dose + 30 days and the next dose and the time more than 30 days after permanent discontinuation to study drug and if occurred the 1st event per patient will be counted. For the primary analysis in this data scope, the time to event for a subject will be censored at the date of the EOMT visit or after no further data collection happened for a subject (e.g. lost to follow-up).

The cumulative incidence function for the event-of-interest as well as the associated competing event(s) together with the corresponding confidence interval will be estimated for each treatment arm using Aalen-Johansen estimators.

The competing event for the primary safety endpoint is death and premature discontinuation of exposure to assigned treatment.

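### The partial-date rule in SAP 4.3 moves an event to first dose or later even when its reported month or year ended before first dose

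*SAP*

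**What the plan says.** SAP section 4.3 covers efficacy events, safety events and adverse events together. With the day missing, the instruction is to "impute the maximum of (date of randomization + 1 week, first date of study intervention, 01.month.year". With only the year known, 1 January of that year replaces the first of the month, and the result may not be later than death. The rules are introduced by "When appropriate, the following rules will be implemented so as not to exclude subjects from statistical analyses due to missing or incomplete data". No criterion for appropriateness follows. Partial dates are listed as recorded.

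The dates feed several definitions:

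- SAP 4.5: "An event is considered treatment emergent if it occurred between start of treatment and not later than 30 days after last administration".
- SAP 6.4.1: "Only events that started after the first dose of study treatment and during the main treatment period are considered for the primary analysis".
- Protocol 9.4.2: "Events that occurred during the pre-treatment period will be displayed in an exploratory manner".
- SAP 6.2.3, 6.4.3 and 6.4.5 plan pre-treatment summaries of efficacy events, safety events and AEs, and 6.4.5 adds a table of AEs during screening.
- SAP 6.2.2 counts efficacy events in the full analysis set (FAS) from randomisation.

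Protocol 8.3.1 collects AEs from consent. SAP section 3 gives "Screening period (visit 1): up to 14 days" and "Pre-treatment period (from visit 2 until visit 4): 7 days". Table 1-1 of the protocol puts first dose on day 8 with a window of +3 days.

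**The concern.** A reported month or year is real information. When that period ended before first dose, the record settles that the event was pre-dose, and no day is needed to classify it. The SAP 4.3 formula uses the reported period only as a candidate for the latest date, so it can push onset later but never before first dose. There is no branch for a period that closed earlier.

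At stake is the correctness of the treatment-emergent tables, which would include events that the site's own record places before dosing, and of the screening and pre-treatment tables, which would omit them. The listings would allow a re-dated event to be traced, but the plan provides no flag in the tables.

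The concern does not extend to the month that contains first dose. A partial date there is truly ambiguous, and assigning it to treatment is a reasonable convention.

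**Working it through.** No figure in the plan depends on this rule, so there is none to reproduce first.

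**1. The formula on three cases**

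| Randomised | First dose | Reported onset | Imputed date |
|---|---|---|---|
| 25 March | 1 April | March | max(1 Apr, 1 Apr, 1 Mar) = 1 April |
| 3 April | 10 April | March | max(10 Apr, 10 Apr, 1 Mar) = 10 April |
| 28 Dec 2020 | 4 Jan 2021 | 2020 | max(4 Jan 2021, 4 Jan 2021, 1 Jan 2020) = 4 Jan 2021 |

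All three events are certainly pre-dose, and all three land on the first-dose date. In the second, March ended before randomisation, so an efficacy event would enter the FAS analysis although it preceded randomisation. The death cap cannot help, because a dosed participant's death follows first dose.

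Applying both formulas to every pre-dose day for a year of randomisation dates gave no imputed date before first dose (for example 0 of 14,600 with consent 13 days before and dosing 7 days after randomisation). With a branch for closed months, all 2,520 provably pre-dose month-and-year records in that scenario stayed pre-dose.

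**2. How often a month has closed**

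Assume first-dose dates spread evenly over 365 days. An event j days before first dose (j ≤ 28) lies in an earlier month for 12j of the 365 dates. Averaged over k pre-dose days, the share is 6(k + 1)/365:

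- k = 7: 48/365 = 0.1315
- k = 14: 90/365 = 0.2466
- k = 24 (14 screening + 7 pre-treatment + 3 window days): 150/365 = 0.4110

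**3. Bleeds**

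Inputs: 600 participants and 10 events per 100 participant-years (Protocol 9.2). The 5-20% missing-day rate is an assumption.

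- Seven days: 600 × 7/365.25 = 11.5 participant-years; × 0.10 = 1.15; × 0.1315 = 0.151; × 0.05 to 0.20 = 0.008 to 0.03 trial-wide.
- All participants given 24 days: 600 × 24/365.25 = 39.4 participant-years; × 0.10 = 3.94; × 0.4110 = 1.62; × 0.05 to 0.20 = 0.08 to 0.32 trial-wide, or 0.03 to 0.11 per group of 200.

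Expected on-treatment bleeds per group, with the plan's loss rate of 15 per 100 participant-years: 200 × 0.10/0.25 × (1 − exp(−0.125)) = 9.40.

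**4. FAS efficacy**

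At 13 per 100 participant-years over 14 screening days: 600 × 14/365.25 = 23.0; × 0.13 = 2.99; × 0.2466 = 0.74; × 0.05 to 0.20 = 0.04 to 0.15 events trial-wide.

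**5. AE composite (illustration only)**

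The documents give no rate. At an assumed 50 to 150 per 100 participant-years over 24 days, the low end is 39.4 × 0.5 × 0.4110 × 0.05 = 0.4 and the high end is 39.4 × 1.5 × 0.4110 × 0.20 = 4.9 misdated trial-wide. About 42.7/200 to 102.1/200 of participants would have an on-treatment event anyway. Net additions per group are then 0.4 × (1 − 0.21)/3 = 0.1 to 4.9 × (1 − 0.51)/3 = 0.8, against 43 to 102 expected.

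**6. Does the event reach the primary analysis?**

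Randomisation is day 1 and dosing is day 8 or later, so randomisation + 1 week is normally no later than first dose, and the imputed date equals the first-dose date. SAP 6.4.1 asks for onset after first dose; SAP 4.5 counts from start of treatment. Read strictly, 6.4.1 excludes a same-day date. The imputed date falls strictly after first dose only if dosing preceded day 8, or if SAP 4.3 reset an unresolved dose date: "If start date and time is recorded as earlier than randomization and cannot be clarified, date and time of randomization will be used". In that case randomisation + 1 week is 7 days after the analysed first dose.

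If the upper-bound bleeds did enter, 0.108 per group, the event ratio would move from 1.50 to (14.10 + 0.108)/(9.40 + 0.108) = 1.494, and from 2.00 to (18.80 + 0.108)/9.508 = 1.989.

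**The case against.** The best defence is the qualifier. A record whose month closed before dosing needs no imputation to keep the subject in an analysis, so the rules could be read as not reaching it. The screening and pre-treatment tables do not say that they use imputed dates, and SAP 4.6 provides for a data assessment at primary completion and at end of study. What stands is that misclassification follows only if the rule is applied as written. But the qualifier names no exemption, this is the only start-date convention in the SAP, and neither the listing nor the data assessment replaces it.

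Missing days should also be uncommon in this window. Visits fall on days 1, 3, 6 and 8, SAEs are reported within 24 hours, and bleeding and thromboembolic events go to adjudication. Eligibility is checked again at visit 2, so some people with such an event during screening would not be randomised. This stands, and makes the bleeding and efficacy figures generous. The missing-day and AE rates are assumptions, so the AE figures are not true bounds.

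A reader might infer that pre-dose events contaminate the primary hazard ratios. The documents do not support this. SAP 6.4.1 requires onset after first dose, the imputed date normally equals first dose, and the two exceptions need a dosing departure or an unresolved date error.

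**Conclusion.** The defect in the rule is certain as a matter of formula; its consequences depend on the rule being applied literally to records of this kind, and the number of such records is unknown. The consequences that follow are wrong counts in the treatment-emergent, screening and pre-treatment tables and, for months that ended before randomisation, in the FAS efficacy analysis.

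The point is minor. The bleeding bound of about 0.1 to 0.3 trial-wide rests on the plan's event rate, a maximal 24-day window for all 600 participants, evenly spread dates and the assumed missing-day rate. Even if those bleeds entered the primary analysis equally in all arms, the pull toward 1 would be negligible beside the plan's stated 90% interval of 0.57 to 2.28. All analyses are descriptive, and no conclusion of the trial is at risk. The plan does leave one wording gap: it does not say how an event imputed to the day of first dose is read under SAP 4.5 and 6.4.1.

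**What to change.** In SAP 4.3, apply the first-dose and randomisation + 1 week terms only when the reported month (or year) is the same as or later than that of first dose. Otherwise keep the event pre-dose:

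- Period ended before randomisation: impute the later of the consent date and the first day of the period, and class the event as screening. In the second case above, with consent on 22 March, this gives 22 March.
- Period contains or follows randomisation: impute the later of the randomisation date and the first day of the period, class the event as pre-treatment by convention, and flag it as imputed. The first case above gives 25 March. The convention is needed because one month can hold both consent and randomisation.

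A record whose period ended before consent should be queried, since AE collection starts at consent and the first branch would otherwise move it forward. Add one sentence so that an event imputed to the first-dose date is treated the same way under SAP 4.5 and 6.4.1.

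SAP 4.4 and 6.5 show that the primary analysis is complete and unblinded. Document this as a post-unblinding correction for the final analysis and list any events reclassified relative to the primary tables. Re-derive those tables only if the list is not empty. The cost is one condition in the text and date code, one sentence and one listing. Version 3.0, which itself describes the primary analysis as completed, and version 4.0 after it already changed data handling in this way.
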